NCT number: Not yet assigned

Protocol ID PI20/1645

Date: December 21, 2021

FGF23 and cardiovascular damage in anemia with or without chronic kidney disease.

CONFIDENTIALITY DECLARATION

The information contained in this document is the property of the promoter and therefore, it is provided confidentially. It may not be disclosed to other people without the sponsor's written authorization, except for the use that may be made of it to obtain the informed consent of the people who are to receive the investigational drug, as well as in communications to the competent health authorities, the Research Ethics Committees or those people who will carry out the study.

GENERAL INFORMATION

A. Identifiers:

- Protocol ID PI20/1645

- Title: **FGF23 and cardiovascular damage in anemia with and without chronic kidney disease.**

B. Treatment group description:

Group 1: Patients with iron deficiency anemia with chronic kidney disease, stages 3, 4 and 5 non on dialysis, treated with oral or intravenous iron for 3 months

Group 2: Patients with iron deficiency anemia with normal renal function, treated with oral or intravenous iron for 3 months

C. Sponsor:

FIBICO (“Fundación para la Investigación Biomédica de Córdoba”)

Hospital Universitario Reina Sofía – Edificio IMIBIC

[name]

[name]

[contact]

Fax: [name]

D. Participants:

Department of Hematology, Internal Medicine and Nephrology of Reina Sofía University Hospital and Maimonides Institute for Biomedical Research of Córdoba (IMIBIC) .

[name]

[name].

PROTOCOL

1. Objectives:

The General Objective of this research project is to evaluate, through in vivo and in vitro studies, the cardiovascular alterations related to the anemia-induced increase in FGF23 production; as well as the identification of possible molecular targets that may be useful in its prevention and / or palliation. This General Objective will be addressed through the following Specific Objectives:

1.- To determine in a population with anemia (due to iron deficiency), with and without chronic kidney disease (CKD), an association between the parameters related to iron metabolism, FGF23 and markers of cardiovascular damage. It will be evaluated:

- 1.1 The levels of FGF23, intact and C-terminal, before and after treatment.
- 1.2 The changes in parameters related to mineral metabolism (calcium, phosphorus, magnesium, PTH, vitamin D, soluble Klotho), inflammation and oxidative stress (IL-12, IL-1b, IL-6).
- 1.3 Markers of cardiovascular damage: BNP, myoglobin, troponin I.
- 1.4 Iron metabolism parameters (ferritin, transferrin saturation index, hepcidin)
- 1.5 MicroRNAs and proteomics expression profile.
- Likewise, although it will not use experimental medication, the safety (side effects) of the iron compounds that are administered will be evaluated.

2- To evaluate in vivo, in a murine experimental model of anemia, with or without CKD, the effects of the modulation (inhibition) of triggers of iron deficiency (hepcidin) and of the increase in FGF23 (HF1 α), on markers of cardiovascular damage. It will be evaluated:

- 2.1. Production of intact FGF23 and C-Terminal FGF23.
- 2.2. Cardiovascular disease markers.
- 2.3. Proteomic profile and differential localization of proteins in situ in cardiac tissue.

3.- To compare in vivo, in an experimental model of anemia with and without CKD, the effect of different I.V. iron presentations (ferrous sulphate, ferric carboxymaltose and ferric citrate) on FGF23 levels and their cardiovascular impact.

4.-To evaluate in vitro, in cardiomyocytes cultures, in the presence of iron deficiency, the direct effect of FGF23 on the induction of cardiac damage. It will be analyzed:

4.1. Gene and protein expression of markers of cardiac damage (myoglobin, troponin and BNP) and hypertrophy.

4.2. The involvement of the PI3K-AKT / GSK3-B-NFAT and FGFR4 / Raf / MEK / ERK signalling pathways.

4.3. Induction of oxidative stress

5.- To evaluate in vitro, in osteoblasts/osteocytes cultures, the direct effect of ferrous sulphate, ferric carboximaltose, ferric citrate and hepcidin on:

5.1. Production of intact FGF23 and C-terminal FGF23.

5.2. Gene and protein expression of intracellular mediators of FGF23 production: DMP1, GALNT3, Phex, FGFR1 and HF1 α .

2. Desing:

2.1: Type: Study in patients: prospective, open, parallel groups.

2.2 Sample size: It is considered that a random sample of 183 individuals for the population of patients with iron deficiency anemia without CKD and 218 for the study to be carried out with patients with anemia and CKD, will be enough to estimate, with a 95% confidence and an accuracy of +/- 5 percentage units, a population percentage that is expected to be around 13% and 15%, respectively. As a percentage of necessary replacements, it is expected to be 5% and 10%, respectively.

3. Study population:

Selection criteria:

This study will include patients who meet all the inclusion criteria and anyone of the exclusion criteria.

Inclusion Criteria:

- Age. 18-85 years old
- Hemoglobin < 11g/dl
- Serum ferritin < 100 ng/ml or transferrin saturation index < 20%
- Written informed consent

Exclusion Criteria:

- Weight < 50 Kg or BMI < 17
- Acute bleeding > 300 ml, within 72 hours before study inclusion
- Proliferative hematologic disease. Hemochromatosis
- Active infections within 30 days before study inclusion
- Systemic inflammatory illness
- HIV, HCV or HBV infection
- Iron active treatment
- Blood transfusion in the last 90 days before inclusion.
- Cardiovascular hospitalization 30 days before study inclusion
- Anticoagulant treatment with coumarinics
- Chronic liver disease
- Immunosupresive therapy
- Erythropoiesis stimulating agents treatment, radiotherapy or quimiotherapy within 30 days before inclusion
- Scheduled major surgery during study period
- Pregnancy or lactation
- Drugs addiction
- Participation in others clinical trials.

Withdrawal criteria:

1. Informed consent withdrawal.
2. Iron treatment intolerance.
3. Medical decision, based on clinical state.

4. Deviation from the protocol, such as intolerance to the treatment or the appearance of new symptoms or pathologies that discourage its continuity.
5. Loss of follow up.

4. Treatment:

Any oral or intravenous iron formulation, prescribed by the responsible clinician. The investigators will not take part in treatment selection.

5. Study procedures:

The total planned duration of the research project for each patient is 3 months. The outpatients of the nephrology, internal medicine and hematology with the possibility of meeting the requirements will be referred to one of the investigators of the research project who will carry out the following visits and procedures:

V0: After the explanation of the research project and the signing of the informed consent in the first screening visit (V0), the patient's history will be evaluated, anthropometric measurements will be taken, and the existing biochemical data will be studied.

V1: One to two weeks after V0, the patient will be summoned to proceed to take blood samples (one hematimetry tube and 2 biochemistry tubes), collection of the morning urine sample, measurement of hemodynamic parameters, from this moment the patients would begin with the oral or intravenous iron therapy indicated by their responsible doctor.

V2: At month 3 (M3) from the start of the study, blood samples (hematimetry and biochemistry), urine and hemodynamic parameters will be taken. Finishing the study.

Patients who present resistance to oral treatment, maintaining Hb <11 and ferritin <100 ng / ml or TSI <20%, may be transferred to the treatment group with IV iron if so decided by their responsible physicians, V3 will then be programmed.

V3: At month 6 (M6) from the beginning of the study, blood samples (hematimetry and biochemistry), urine and hemodynamic parameters will be taken. Finishing the study.

6. Statistic analysis

Data that follow a Normal distribution will be described as mean \pm standard deviation and non-Normal data will be described as median with interquartile range. The primary end point will be compared between the two treatment groups using an unpaired Student's t-test (possibly after log transformation if the data does not follow a Normal distribution) and as an intention to treat. Changes and differences between groups in secondary end points will be analyzed using paired and unpaired Student's t tests or Wilcoxon and Mann-Whitney tests for continuous variables, and Chi-square or Fisher's exact test for dichotomous variables. Linear mixed models will be used to analyze variables with repeated measures. Linear and logistic regression analyzes with adjustment for various covariates will be applied to the baseline data to investigate any association with the change in various parameters, as well as any association with clinical events.

7. Workplan

The total planned duration of the research project is 1 YEAR, from the inclusion of the first patient:

- 7.1- Start of the study: After obtaining the favorable opinion of the CEI, it is expected to include the first patient in the first quarter of 2022.
- 7.2- Period of recruitment / inclusion of patients: 6 months (between January 2022 and June 2022).
- 7.3- Treatment period: each patient included will receive treatment for 3 months (January 2022-January 2023).
- 7.4- Completion of the study: last contact of the last patient included.
- 7.5- Statistical analysis and writing of the final report.

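### Does the eligibility sentence in section 3 really admit patients who meet an exclusion criterion?

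*Protocol*

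**What the plan says.** Section 3 of the protocol (Study population, Selection criteria) opens with one sentence on how its two lists are to be used: "This study will include patients who meet all the inclusion criteria and anyone of the exclusion criteria". A list of 4 inclusion items follows, and then a list of 17 items under the heading Exclusion Criteria. One of the 17 is "Iron active treatment".

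Section 5 describes V1 as the visit at which blood and urine are collected and haemodynamics measured. It then says that "from this moment the patients would begin with the oral or intravenous iron therapy indicated by their responsible doctor". Objective 1.1 in section 1 concerns "The levels of FGF23, intact and C-terminal, before and after treatment", and section 6 plans paired and unpaired tests for the secondary end points.

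Neither list in section 3 mentions renal status. The two groups are defined in section B of the general information: "Group 1: Patients with iron deficiency anemia with chronic kidney disease, stages 3, 4 and 5 non on dialysis" and "Group 2: Patients with iron deficiency anemia with normal renal function, treated with oral or intravenous iron for 3 months".

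**The concern.** Eligibility is protocol content, and a statistical analysis plan would not be expected to repair it. The sentence is grammatically complete, so a word lost in reading the PDF is an unlikely explanation. At face value it makes an exclusion condition a requirement for entry and shuts out every patient who has none.

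If anyone followed it, the analysis could suffer. V0 lists no blood draw, only history, anthropometry and a review of existing results, so V1 supplies the study's own pre-treatment sample. A patient already taking iron would give that sample on treatment. The before-and-after comparison of FGF23 in objective 1.1, the iron parameters in objective 1.4 and the paired analyses in section 6 would then not start from an untreated value for that patient. The list also contains items, such as pregnancy and participation in other trials, whose direction should not be open to doubt.

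**Working it through.** No figure in the protocol rests on this sentence, so the main check sets the passages side by side under each reading.

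**Inputs.** The introductory sentence and the two lists come from section 3 (4 inclusion items, 17 exclusion items, by count). The timing of sampling and iron is from section 5, the aims from section 1, the group definitions from section B, and the sample-size inputs from section 2.2.

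**Literal reading: at least one exclusion item must be met.**

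- It contradicts the heading of the list it refers to, for all 17 items.
- It would bar any patient with iron deficiency anaemia who is free of all 17 conditions. Section 1 and section B describe the population as iron deficiency anaemia with or without chronic kidney disease, and nothing there calls for one of these conditions.
- Through the item on current iron treatment it would also admit patients for whom iron cannot begin at V1. It would permit such patients but would not require them, because any of the other 17 − 1 = 16 items would satisfy the sentence.

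**Intended reading: no exclusion item may be met.**

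- The heading and the list agree.
- Excluding patients on iron agrees with sampling at V1 and starting iron from that point.
- The before-and-after aim in objective 1.1 has its untreated V1 value.
- The group definitions in section B apply without conflict.

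The first reading defeats itself on the page where it occurs. The second agrees with every other passage. The apparent clash between the sentence and V1 is therefore no separate defect. It exists only under the reading that the heading already rules out, and the V1 timing is further evidence of what was meant.

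**Is a language slip a credible explanation?** The same pages contain 'Desing', 'quimiotherapy', 'Immunosupresive' and 'others clinical trials'. A wrong pronoun in such a text is more likely to be weak English than a rule fixed in reverse.

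**Do the stated sample sizes depend on it?** Section 2.2 gives 95% confidence, precision of ±5 percentage points, expected percentages of 13% and 15%, and replacement of 5% and 10%. With n = z² p(1 − p)/d², z = 1.96 and d = 0.05, divided by (1 − replacement):

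| Group | p | n before replacement | Divisor | Result | Stated |
|---|---|---|---|---|---|
| Without CKD | 0.13 | 3.8416 × 0.1131 / 0.0025 = 173.8 | 0.95 | 182.9 | 183 |
| With CKD | 0.15 | 3.8416 × 0.1275 / 0.0025 = 195.9 | 0.90 | 217.7 | 218 |

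Both stated sizes reproduce. The eligibility sentence enters neither the formula nor its inputs.

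**The case for a change.** The strongest case for acting is that this is the only sentence saying how the lists combine. Section 5 speaks only of outpatients who may meet the requirements, which leads back to section 3. A rule that governs safety-relevant items should be right as written, without the reader having to invert it, and the repair would be a single word.

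Part of this stands. The sentence is wrong, nothing else in the document restates the rule, and correcting it would cost almost nothing. What does not stand is any consequence for the trial. To show harm one would need a reader who takes a list headed as exclusions for a list of entry requirements, and who then enrols patients already on iron into a study whose procedures start iron at V1. The protocol gives no ground for expecting that. The argument about a lost untreated baseline depends wholly on the reading that everyone would reject.

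A related suggestion is to add a pointer to renal status in section 3, since neither list mentions it. Section B already defines both groups by renal function, and section 2.2 repeats the split with and without CKD. A pointer would repeat what is there and settle no open question.

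**Conclusion.** The wording is wrong, but it needs no change to the plan. It is a clerical slip of one word: 'anyone' stands where 'none' is meant. The heading of the list and the start of iron at V1 leave a single workable rule, and site staff and analysts would apply that rule without being told. Correcting the word would alter neither who is enrolled, nor the V1 values, nor the sizes of 183 and 218, nor any analysis in section 6. It can be tidied if the document is reissued for another reason.

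The conclusion assumes that screening follows the ordinary meaning of an exclusion list. The protocol contains nothing against that assumption. It would change only if patients had in fact been screened by the literal sentence, which the document cannot show either way.

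### The withdrawal list does not separate stopping iron from leaving the study, so month-3 samples may be lost selectively in patients who react to iron; the expected bias is modest

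*Protocol*

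**What the plan says.** Protocol section 3 (Study population, Withdrawal criteria) gives five numbered items under one heading:

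- Items 1 and 5 end participation by their nature: "Informed consent withdrawal" and "Loss of follow up".
- Items 2, 3 and 4 mainly concern the treatment or the patient's condition: "Iron treatment intolerance", "Medical decision, based on clinical state" and "Deviation from the protocol, such as intolerance to the treatment or the appearance of new symptoms or pathologies that discourage its continuity". Intolerance therefore appears twice, the second time as an example of a protocol deviation.

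Section 5 (Study procedures) sets the follow-up measurement: "V2: At month 3 (M3) from the start of the study, blood samples (hematimetry and biochemistry), urine and hemodynamic parameters will be taken". It describes no early-termination visit and does not say whether a withdrawn patient attends V2. The only extra visit, V3 at month 6, is for patients resistant to oral iron who are moved to intravenous iron.

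Objective 1.1 in section 1 concerns intact and C-terminal FGF23 before and after treatment. Section 6 attaches "and as an intention to treat" to the primary comparison. For the rest it says "Changes and differences between groups in secondary end points will be analyzed using paired and unpaired" t tests or rank-based equivalents, and it adds linear mixed models for repeated measures. Section 2.2 allows for replacements of 5% (without CKD) and 10% (with CKD).

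**The concern.** Stopping a treatment and leaving a study are different events. A list that merges them under withdrawal leads site staff to treat a patient who stops iron as a patient who has left. V2 is the only after-treatment measurement for most patients, so such a patient would have a V1 value and nothing later.

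The loss would not be random. It would fall on patients who tolerated iron badly, developed new symptoms or were taken off treatment on clinical grounds. Their change in FGF23, inflammation or cardiac markers could plausibly differ from that of patients who completed three months of iron. The before/after results would then describe mainly those who tolerated iron. An analysis plan can choose how to handle missing values, but it cannot create a month-3 sample that was never drawn.

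**Working it through.** **1. The texts side by side.** The list stands under Study population, not under Treatment, and its heading is withdrawal. Section 5 provides continued follow-up for one treatment problem (resistance to oral iron) and none for intolerance. Both points favour reading items 2–4 as study exit. Against this, V2 is timed from the start of the study and is not conditional on still taking iron. The protocol neither requires nor forbids V2 after iron stops, so study exit is the plain reading but remains an inference.

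**2. The plan's own figure.** Inputs from section 2.2: 95% confidence, ±5 points, expected percentages 13% and 15%, replacements 5% and 10%, stated sizes 183 and 218. Formula: n = 1.96² p(1−p)/0.05², then divide by (1 − replacement rate).

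- Without CKD: 1.96² × 0.13 × 0.87/0.05² = 173.8; 173.8/0.95 = 182.9, stated 183.
- With CKD: 1.96² × 0.15 × 0.85/0.05² = 195.9; 195.9/0.90 = 217.7, stated 218.

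The stated sizes reproduce, so the allowance is built in.

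**3. Patients covered by the allowance.** 0.05 × 183 = 9.15 and 0.10 × 218 = 21.8, together 30.95 of 401 (7.7%), taken here as losses from all causes. About 174 and 196 patients keep a V2 value, which meets the stated ±5 points.

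**4. Losses due to items 2–4.** The protocol does not give this share. Assume s = 25%, 50% or 75%: 2.3, 4.6 or 6.9 patients without CKD and 5.5, 10.9 or 16.4 with CKD.

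**5. Shift in the within-group mean change.** Let L be the total loss and D the assumed difference in mean change, in SD units, between patients lost through items 2–4 and completers. Take other losses as unrelated to outcome. Had patients who stopped iron attended V2, they would make up sL/(1 − (1−s)L) of those measured. The completer mean is therefore off by D × sL/(1 − (1−s)L).

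| Group | D | s = 25% | s = 50% | s = 75% |
|---|---|---|---|---|
| Without CKD, L = 0.05 | 1 SD | 0.013 | 0.026 | 0.038 |
| Without CKD, L = 0.05 | 0.25 SD | 0.003 | 0.006 | 0.009 |
| With CKD, L = 0.10 | 1 SD | 0.027 | 0.053 | 0.077 |
| With CKD, L = 0.10 | 0.25 SD | 0.007 | 0.013 | 0.019 |

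Standard error of a mean change, in SD units: 1/√174 = 0.076 and 1/√196 = 0.071.

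**6. Shift in the between-group difference, D = 1 SD.** With unequal shares it runs from 0.027 − 0.038 = −0.011 to 0.077 − 0.013 = 0.064 SD. The standard error is √(1/174 + 1/196) = 0.104 SD.

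**The case against.** Four objections carry weight.

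**The text is unclear; it does not order sampling to stop.** A reader might infer that the protocol removes intolerant patients before V2. It does not say so, and the timing of V2 allows the opposite reading. This stands. What is established is wording that permits two ways of handling the same patient, with the heading favouring exit.

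**Intention to treat.** A reader might infer a general contradiction with the intention-to-treat statement. The documents do not support that. Section 6 attaches the principle only to the primary comparison, and the groups are defined by CKD status, not randomised, so leaving early does not change a patient's group. What remains is narrower: the intention-to-treat analysis would be incomplete if the primary end point needs a month-3 value, and the protocol does not name that end point.

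**The planned mixed models.** Paired tests drop a patient with only V1, but the linear mixed models in section 6 can keep that patient. This is real mitigation. It is valid only if loss depends on what was observed. A reaction to iron arises after V1, and V2 is the next planned measurement, so the data offer little to support that assumption.

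**Size and target.** The shifts are mostly below the standard errors, and a before/after result in patients who actually received iron is a defensible target for a mechanistic study. Both points hold and lower the severity. Neither shows that the samples should go uncollected: with V2 taken and the stopping date recorded, both results can be reported.

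**Conclusion.** The point holds at low severity. The protocol does not separate stopping iron from ending participation and does not say whether V2 applies after iron stops. On the plain reading, month-3 values would be missing selectively in patients who react to iron.

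The expected bias is modest. Only the corner with a 75% share and a 1 SD gap in the CKD group (0.077) exceeds its standard error (0.071), and the between-group shift stays below its own. These figures rest on the stated allowance covering all losses, an assumed 25–75% share for items 2–4, an assumed gap of 0.25–1 SD, and other losses being unrelated to outcome. The protocol gives neither the share nor the gap. The bias would grow if actual losses exceeded the allowance, and enrolling more patients would not remove it.

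A reader might also infer a loss of precision. The arithmetic does not support that, since the allowance already covers it.

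**What to change.** In section 3, state which listed events end study participation. In section 5, state that patients who only stop or change iron, a decision left to the responsible clinician, still have the planned V2 blood, urine and haemodynamic measurements unless consent is withdrawn or contact is lost. Record the date of and reason for stopping, so that results can also be shown for those who completed treatment. Merging the two intolerance entries is editorial only.

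The cost is protocol wording, one date and one reason per patient who stops, and the already planned V2 for those patients. That is at most about 31 of 401 under the stated allowance, and fewer in practice because some losses will be consent withdrawal or lost contact. The downside is that some patients who stopped iron attend one visit that was already planned. No treatment decision changes.

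### Does the month-6 visit, held only for oral-iron non-responders moved to IV iron, undermine the paired tests and mixed models?

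*Protocol*

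**What the plan says.** Section 5 of the protocol takes study samples from every patient at V1 and again at V2, month 3, where the study ends for most. One exception follows. Patients on oral iron whose haemoglobin stays below 11 with ferritin below 100 ng/ml, or transferrin saturation below 20%, "may be transferred to the treatment group with IV iron if so decided by their responsible physicians, V3 will then be programmed". That extra visit is "V3: At month 6 (M6) from the beginning of the study", with the same sampling as V2.

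Section 6 states for secondary endpoints: "Changes and differences between groups in secondary end points will be analyzed using paired and unpaired" Student's t tests or their rank-based counterparts. It adds: "Linear mixed models will be used to analyze variables with repeated measures". No visit is named in either sentence.

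On duration, section 5 says "The total planned duration of the research project for each patient is 3 months", section 7.3 says "each patient included will receive treatment for 3 months", and item B of the general information describes group 2 as "Patients with iron deficiency anemia with normal renal function, treated with oral or intravenous iron for 3 months". Group 1 (CKD) carries the same 3-month limit.

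**The concern.** V3 depends on outcome and on treatment. Oral responders, patients started on IV iron, and resistant patients who were not switched have no month-6 data. Month 6 is therefore fully confounded with non-response and change of route.

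If V3 went into the section 6 analyses without distinction, three things could go wrong.

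- A month-6 term could be read as a result for the whole CKD or non-CKD group when it rests on a selected, re-treated subset.
- For FGF23 or cardiac markers, a model that omits the haemoglobin and iron values driving selection could give a biased month-6 term.
- A raw V2-to-V3 change in haemoglobin, ferritin or transferrin saturation would partly be regression to the mean, and the IV switch would get the credit.

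Coding time as linear would also let the V3 values affect the month-3 change.

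**Working it through.** **1. Sample size, for scale.** Section 2.2 plans "a random sample of 183 individuals for the population of patients with iron deficiency anemia without CKD and 218" for those with CKD. Formula: n = 1.96² × p(1 − p) / 0.05², divided by one minus the replacement rate.

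- p = 0.13: 3.8416 × 0.1131 / 0.0025 = 173.8; 173.8 / 0.95 = 182.9, so 183.
- p = 0.15: 3.8416 × 0.1275 / 0.0025 = 195.9, rounded up to 196; 196 / 0.90 = 217.8, so 218.

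Both figures reproduce. Evaluable total: 174 + 196 = 370. The protocol does not say what share would reach V3.

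**2. Regression to the mean in haemoglobin.** Assumptions, none from the protocol: no true change from month 3 to month 6, between-person SD 1.2 g/dl, within-person SD s_w, month-3 mean m, and selection on the month-3 value being below 11. Let S² = 1.2² + s_w², r = 1.2²/S² and z = (11 − m)/S. The expected rise is (1 − r) × S × φ(z)/Φ(z).

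| m | s_w | S | r | z | S·φ/Φ | Rise (g/dl) | Back above 11 |
|---|---|---|---|---|---|---|---|
| 11.5 | 0.4 | 1.265 | 0.900 | −0.395 | 1.348 | 0.135 | 19% |
| 12.5 | 0.8 | 1.442 | 0.692 | −1.040 | 2.246 | 0.691 | 49% |

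A second set of assumptions gives a similar range. With total SD 1.2, mean 11.8 and 60% on oral iron, z = −0.667 and S·φ/Φ = 1.518. Multiplying by (1 − correlation) gives 0.76, 0.46 and 0.15 g/dl for correlations 0.5, 0.7 and 0.9. The share reaching V3 is 0.60 × 0.252 = 15%.

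The mechanism is real, but this figure is for haemoglobin. Section 1 lists FGF23, mineral metabolism, inflammation, cardiac markers, ferritin, transferrin saturation, hepcidin, microRNAs and proteomics. Haemoglobin appears only as an entry and switching criterion. Ferritin and transferrin saturation are listed and face the same threat, but no size was worked out for them.

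**3. FGF23 at month 6 in a mixed model.** The simulation used 370 patients, 60% on oral iron, all oral patients below 11 switched, no switch effect, and a true change of −0.40 log units. The assumed correlation between haemoglobin and FGF23 responses ran from 0 to 0.7.

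- Random intercept: month-6 term −0.40 to −0.23, so 0 to 42% too small.
- Unstructured covariance: −0.40 to −0.33, so 0 to 18% too small.

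The bias vanishes when the two responses are unlinked. The simulation ignored the ferritin/transferrin condition and physician discretion. It had no renal-group term, so it says nothing about bias in the CKD versus non-CKD comparison.

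**4. Month 3.** With visit as a factor, the month-3 coefficient equalled the raw V2 − V1 change (−0.40) in every scenario. This is expected when V1 and V2 are complete. Under a random intercept, the V2 − V1 contrast is uncorrelated with V1 + V2 and with V3. Under unstructured covariance, a V3 that is missing given V1 and V2 leaves the first two means at their sample values. Only linear time moved it, to −0.27 to −0.31 per 3 months with an assumed plateau after month 3. The protocol states no such coding.

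**5. Text side by side.** The group definitions, per-patient duration, the end of study at V2 and the 3-month treatment period in section 7.3 all fix month 3. V3 is mentioned only in section 5, as follow-up of switched patients. The calendar has room for it: recruitment ends in June 2022 and the treatment window runs to January 2023.

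**The case for a change.** The best argument for acting starts from the sampling schedule. Without V3 each patient has two study samples, which paired tests already handle, so V3 is the only third measurement a mixed model could take in. V2 and V3 are both described as the end of the study, and objective 1.1 asks for FGF23 before and after treatment, so for a switched patient the after value might be month 3 or month 6. A mixed model does not rescue a group-wide month-6 mean either, since unswitched patients have no chance of a V3.

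Some of this stands. A group-wide month-6 mean would be extrapolation, and a V2-to-V3 gain in the selecting variables would need a caveat. The step from there to a fault in the plan does not. A mixed model with two visits and a group-by-visit term is routine, and it keeps patients who miss V2, so the sentence in section 6 does not imply that V3 is pooled. The 3-month group definitions give the natural reading of the after value. The harm needs an analyst to present a visit held only for switched patients as a result for everyone, or to code time linearly. The protocol proposes neither.

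**Conclusion.** No change to the plan is needed. V3 values describe oral-iron non-responders moved to IV iron and should be read that way. The sentence that creates the visit already says who attends it. Section 6 states no group-wide month-6 analysis. The primary t-test is not in question, and month-3 estimates hold with visit as a factor. Choice of visits, coding of time and covariance structure are commonly settled in an SAP, which may exist but is not shown.

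The sizes above (0.13 to 0.69 g/dl for haemoglobin; 0 to 42% for FGF23) rest wholly on assumed inputs and apply only to a month-6 reading that the protocol does not announce. Setting V3 aside from all inferential models would also give up data without improving the month-3 results.

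The 3-month duration statements do not fit literally with a month-6 visit, and the passages must be reconciled in wording. V3 is written as an exception, so this is a clerical matter that changes no analysis. Labelling V3 as descriptive follow-up of switched patients would be a harmless optional clarification.
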